5.3 Screen Failures

Screen failures are defined as patients who consent to participate in the clinical trial but are not eligible for participation according to inclusion/exclusion criteria. A minimal set of screen failure information is required to ensure transparent reporting of screen failure patients to meet requirements from regulatory authorities. Minimal information includes demography, screen failure details and eligibility criteria.

If the patient has failed the inclusion criteria or fulfilled one of the exclusion criteria related to lab values or pathology analysis, only one re-sampling of the relevant parameter within 2 weeks is allowed if the result is expected to fall within the timeframe limit. However, in case of technical issues (e.g. haemolysed or lost samples), resampling is allowed for the affected parameters or pathology samples. If a timeframe longer than 2 weeks is required for analysis, the patient must be re-screened; all screening assessments must be repeated (including laboratory parameters) and the patient must be reconsented. Screening bone marrow results may be used if the subject is reconsented within 90 days of the latest bone marrow procedure.

If the patient has failed any other inclusion criterion, or fulfilled any other exclusion criterion, resampling/rescreening is not allowed.

38 of 77

6.0 STUDY INTERVENTION, CONCOMITANT THERAPY, AND PRECAUTIONS

6.1 Clinical Trial Material

Intervention Name	Etavopivat
Туре	drug
Dose Formulation	tablet
Unit Dose Strength	200 mg
Dosage Level	two tablets daily
Route of Administration	oral
Use	experimental
Sourcing	Sponsor
Appearance	film coated, oval-shaped tablets
Packaging and Labeling	blister pack

See the Study Pharmacy Manual for additional detail.

6.2 Preparation/ Handling/ Storage/ Accountability

All study drugs will be transported, received, stored, and handled strictly in accordance with the container or product label, the instructions supplied to the research site and its designated pharmacy, the site's standard operating procedures (SOPs), and applicable regulations. Appropriate storage temperature and transportation conditions will be maintained for the study drug from the point of manufacture up to delivery of the study drug.

Upon receipt by the study site, the study drug will be promptly transferred to the appropriate environmentally controlled storage area. The research pharmacy staff will examine the shipment and temperature monitoring devices, if applicable, to verify that the study drugs were received in acceptable condition. Once inspected, the study drug will be stored in a secure area with access restricted to authorized research pharmacy staff, under physical conditions consistent with the investigational product's specific requirements.

The research site's pharmacist or delegate is responsible for ensuring that all study drug received at the site is inventoried and accounted for throughout the study, according to applicable regulations and the site's SOPs. All original containers, whether empty or containing study drug will be returned to the pharmacy. Study drug returned by study patients will be stored and disposed of according to the Sponsor's instructions. Contents of the study drug containers will not be combined. Unused study drug and study drug returned by the patients will be available for verification by the Sponsor's site monitor. See the Study Pharmacy Manual for additional detail, including reporting of Product Complaints.

6.3 Study Drug Administration

Etavopivat may be taken with or without food. Each dose should be taken with a glass of water. Subjects should be instructed to take their daily dose at approximately the same time each day except for dosing on in-clinic visiting days.

6.4 Study Intervention Compliance

Patients will be asked to return their unused study drug as well as their empty drug packets at each clinic visit. The study site will record the number of pills dispensed and the number returned at each visit, thereby assessing compliance.

6.5 Treatment of Overdose

For this study, any dose of etavopivat greater than the intended dose will be considered an overdose (see also Section 8.7.11). There is no known antidote for etavopivat. Should an overdose occur, the patient should be treated with appropriate supportive care based on medical judgment.

As described in Section 8.7.11, in the event of an overdose, the Investigator should:

- Monitor the patient for any AE/SAE and laboratory abnormalities
- Document the quantity of the excess dose as well as the duration of the overdose
- Complete the Special Situations Report form and fax/email to Novo Nordisk Global Safety within 24 hours of knowledge of the event (as outlined in Section 8.7.11)

6.6 Missed Dose

Subjects will be instructed that if they miss a dose by 12 or more hours after the scheduled dosing time, they should skip the dose and take the next dose of study drug as scheduled.

6.7 Concomitant Therapy

6.7.1 Concomitant Medications

All medications taken by patients from Screening until the completion of the Safety Follow-up visit will be documented as concomitant medications. The reported medications will be reviewed and evaluated by the Investigator to determine if they affect a patient's eligibility or continued participation in the study.

Patients are required to avoid starting new non-prescription medicine within 14 days to first study dose and throughout the study, unless discussed with the investigator. The use of St John's wort should be avoided in this period.

Strong inducers of CYP3A4/5 (see Appendix F) are prohibited during the study.

With the exception of strong inducers of CYP3A4/5, concomitant prescribed medications are allowed for patients if prescribed by the Investigator to treat clinical events or exempted by the Medical Lead on a case-by-case basis because they would be unlikely to affect the study results or patient safety.

Use of erythropoietin or thrombopoietin mimetics are prohibited during the study and within 30 days prior to starting study treatment, with the exception of erythropoietin (ESA) in patients with diagnosed stage 3 or 4 CKD and who had been on a stable ESA dose for ≥6 months and plans to continue ESA at the same dose throughout the duration of the study. Hematopoietic growth factors for the treatment of transient neutropenia may be used when clinically indicated.

Current use of luspatercept is prohibited during the study and within 30 to 80 days before starting study treatment (based on transfusion history).

40 of 77

6.8 Precautions

Because etavopivat is an investigational agent in development, all possible side effects are not yet known. Please refer to the etavopivat Investigator's Brochure for additional Warnings and Precautions.

6.8.1 Childbearing Potential

Female patients of child-bearing potential must have a negative serum pregnancy test during the Screening period. Urine pregnancy testing may be performed locally if indicated during the study. If a urine pregnancy test is positive, the result must be confirmed with a serum pregnancy test.

Female patients may not be pregnant, lactating, or breast-feeding or plan to become pregnant (including ova donation) within 90 days of last study drug administration.

Female patients will be considered of childbearing potential after the onset of their first menstrual period. For all patients of childbearing potential, acceptable methods of contraception including abstinence, must be in use from the time of consent through the final study visit, and for 90 days after the last dose of study drug. Patients who are not sexually active during the Screening Period must agree to the contraceptive requirements if they become sexually active with a partner of the opposite sex during the study and for 90 days after the last dose of study drug.

Adult female patients are deemed of non-childbearing potential if they are either surgically sterile (hysterectomy, bilateral tubal ligation, salpingectomy, and/or bilateral oophorectomy at least 26 weeks (182 days) before the Screening visit) or are post-menopausal, defined as spontaneous amenorrhea for at least 2 years, with follicle-stimulating hormone in the post-menopausal range at the Screening visit.

It should be noted, that based on nonclinical toxicity studies no effect on fertility and embryofetal development have been observed. Based on the non-clinical data, the safety committee endorsed the category for the Embryo-fetal risk assessment: Unlikely risk of human teratogenicity/fetotoxicity.

6.8.1.1 Contraception Guidelines

Sexually active female patients of childbearing potential and sexually active male patients must use an acceptable method of contraception, as a minimum, during their participation in the study from the time of consent until 90 days after the last administration of study drug. If a patient prefers to use more highly effective forms of birth control, that is allowed.

Acceptable methods of contraception under this protocol are listed below. Periodic abstinence (calendar, symptothermal, postovulation methods), withdrawal (coitus interruptus), spermicides only, and lactational amenorrhoea method are not acceptable methods of contraception.

Male patients

Male patients who can father a child and are sexually active must agree to use at least an acceptable effective method of contraception, which includes:

- Abstinence: abstinence can be used, when in line with the preferred and usual lifestyle of the patient.
- Male condom

• If a male patient confirms that his female partner(s) is not of childbearing potential (ie, post-surgical sterilization, as defined above) or is using an acceptable method of contraception, this is acceptable as the only means of contraception.

Examples of acceptable methods of contraception for male patients' female partner(s) are listed in Table 6-1.

Male patients with documented infertility or surgical sterilization (performed at least six months before the first dose of study drug) are exempt from the contraception requirement. Infertility may be documented through examination of a semen specimen or by demonstration of the absence of the vas deferens on ultrasound before the first dose of study drug (W1D1).

Female patients

Female patients of childbearing potential must agree to use an acceptable method of contraception, as a minimum, consistently and correctly, as described in Table 6-1.

As a minimum, contraception should be maintained until 90 days after treatment discontinuation.

Table 6-1 Acceptable contraceptive methods

CONTRACEPTIVES^a ALLOWED DURING THE TRIAL INCLUDE:

ACCEPTABLE METHODS^b

- Progestogen-only oral hormonal contraception where inhibition of ovulation is not the primary mode of action
- Male or female condom with or without spermicide^c
- Cervical cap, diaphragm, or sponge with spermicide
- A combination of male condom with either cervical cap, diaphragm, or sponge with spermicide (double barrier methods).

NOTES

- a. Contraceptive use by men or women should comply with local regulations regarding the use of contraceptive methods for those participating in clinical studies.
- b. Considered effective, but not highly effective failure rate of ≥1% per year. Periodic abstinence (calendar, symptothermal, post-ovulation methods), withdrawal (coitus interruptus), spermicides only, and lactational amenorrhoea method (LAM) are not acceptable methods of contraception.
- c. Male condom and female condom should not be used together (due to risk of failure with friction).

7.0 DISCONTINUATION OF STUDY INTERVENTION AND PARTICIPANT DISCONTINUATION/ WITHDRAWAL

A patient may be discontinued at any time during the trial at the discretion of the investigator for safety, behavioural, compliance or administrative reasons. If a patient is prematurely discontinued from participation in the study prior to Week 48, the Investigator or designee must make every effort to perform the assessments scheduled for the EOT visit (W48D1) and schedule a Safety Follow-up visit 28 days after last study treatment. (see Table 1.2).

The Investigator will document the reason(s) for study drug discontinuation on the electronic case report form (eCRF) and the patient's source medical record. Patients who permanently discontinue the study treatment should be encouraged to continue participating in safety follow-up. Only patients who withdraw consent will be considered as withdrawn from the trial. Once a patient permanently discontinues study treatment, they may not be retreated.

7.1 Dose Modification / Discontinuation of Study Intervention

7.1.1 Adverse Event Interruption/Stopping Criteria

Criteria for treatment interruption, dose reduction, and treatment discontinuation due to AEs will be assessed at the investigator's discretion (see Section 8.7.6 and Section 8.7.7). Specific reporting criteria for liver enzyme abnormalities are provided in Section 8.7.2

Table 7-1 Suggested Dose Modifications for Treatment Related AEs

Severity	Non-Hematologic	Hematologic
Grade 3	Hold treatment until recovery to ≤ G1 or baseline, whichever is worse ^b , then resume at the next lower dose level (50% reduction). Contact Medical Monitoring if resumption of etavopivat at full dose is clinically indicated.	Continue treatment at the same dose. If dose interruption is clinically indicated, resume dosing at same dose level after recovery to \leq G2 or baseline, whichever is worse.
Grade 4	Permanently discontinue treatment ^c	Hold treatment until recovery to ≤ G2 or baseline, whichever is worse, then resume at the next lower dose level. Contact Medical Monitoring if resumption of etavopivat at full dose is clinically indicated.

a. In the event of Grade 3 nausea, vomiting, diarrhea, or rash, the patient can continue at the same dose if the patient is responsive to treatment measures within 72 hr.

b. A patient with a Grade 4 AE may resume treatment at the next lower dose level if the AE recovers to Grade 0-1 or baseline and if in the opinion of the Investigator and Sponsor, the patient can be monitored for recurrence of AE.

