7.1.2 Study Intervention Restart or Rechallenge after Stopping Criteria Met

Patients who require treatment interruption > 28 days for a related AE will be withdrawn from the study.

Patients who require a dose reduction after recovery from the AE causing a treatment interruption should be seen in clinic. At the Investigator's discretion, restarting a patient's study treatment at the modified dose prior to a clinic visit using the patient's previous study treatment supply is allowed. However, the rationale and instructions for how the patient should modify their daily dose of study treatment should be documented.

After a dose reduction, if treatment is tolerated at the reduced dose for ≥ 14 days, a dose increase to the original dose is allowed (i.e., rechallenge). Patients should be seen in clinic and receive a new supply of study treatment reflecting the modified dose. Rechallenge without a clinic visit is not allowed, unless discussed with the Medical Monitor. Recurrence of the same AE after a rechallenge should follow the dose interruption/modification steps outlined above. However, in these cases if the AE recurred within 4 weeks of the rechallenge, a subsequent dose increase is not allowed.

A new Grade 3 or higher AE occurring while the patient is receiving a reduced dose should require treatment discontinuation. Discussion with the Global Medical Monitor is required before restarting treatment.

Treatment discontinuation may be required if the AE causing the dose interruption and dose reduction re-occurs at Grade 2 or higher while the patient is receiving the reduced dose. Discussion with the Global Medical Monitor is required before restarting treatment.

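### Protocol 7.0, Table 7-1, 7.1.2, 7.2.1 and 7.2.2 conflict on stopping and restarting in three situations, two of which can change who stays on drug

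*Protocol*

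**What the plan says.** Protocol 7.1.1 opens with a discretion clause: "Criteria for treatment interruption, dose reduction, and treatment discontinuation due to AEs will be assessed at the investigator's discretion". The title of Table 7-1 presents its contents as suggestions and limits them to treatment-related events.

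- **Grade 4 non-hematologic.** The Table 7-1 cell reads "Permanently discontinue treatment". A footnote reads "A patient with a Grade 4 AE may resume treatment at the next lower dose level", on condition of recovery and of the Investigator's and Sponsor's opinion that the patient can be monitored. Section 7.0 reads "Once a patient permanently discontinues study treatment, they may not be retreated".
- **New event on a reduced dose.** Section 7.1.2 reads "A new Grade 3 or higher AE occurring while the patient is receiving a reduced dose should require treatment discontinuation". Its next sentence requires discussion with the Global Medical Monitor before a restart. Section 7.2.1 defines treatment discontinuation as a permanent stop. For a Grade 3 hematologic event, Table 7-1 reads "Continue treatment at the same dose".
- **Long interruption.** Section 7.1.2 reads "Patients who require treatment interruption > 28 days for a related AE will be withdrawn from the study". Section 7.2.1 lists the same event among the mandatory reasons to stop treatment. Section 7.2.2 does not list it among the reasons for leaving the study. Section 7.0 reads "Only patients who withdraw consent will be considered as withdrawn from the trial".

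**The concern.** These rules govern what happens after severe or prolonged toxicity. Where they disagree, two sites can each follow the text and handle the same patient differently.

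The analysis is exposed in two ways. First, the Efficacy Evaluable Set (Protocol 9.2, SAP 2.1) contains only patients who completed the Week 24 Response visit, and SAP 4.2.1.1 uses it as the denominator of the primary response rate. Under 7.2.1, a patient who stops early has the end-of-treatment visit at that time, followed by safety follow-up. A decision to stop or restart before Week 24 can therefore decide whether the patient is in the primary analysis. Second, premature discontinuations are a secondary endpoint (SAP 1.1.1.2), and SAP 4.1.1 tabulates treatment and study discontinuations with their reasons. The meaning of those tables depends on how section 7 classifies each patient.

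**Working it through.** The plan states no figure for this point, so the check is a comparison of the rules.

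| Situation | Rule A | Rule B | Can both be followed? |
|---|---|---|---|
| Related Grade 4 non-hematologic AE | Permanent stop (Table 7-1 cell), no retreatment (7.0) | Resume at the next lower dose level after recovery (Table 7-1 footnote) | Not as written: 7.0 states no exception |
| New Grade 3 or higher AE on a reduced dose | Treatment discontinuation (7.1.2), permanent by definition (7.2.1), no retreatment (7.0) | Restart after discussion with the medical monitor (7.1.2, next sentence) | No, if the term has its 7.2.1 meaning |
| The same, if a related Grade 3 hematologic AE | Treatment discontinuation (7.1.2) | Same dose (Table 7-1, no exception for patients already reduced) | No, and no precedence is stated |
| Related-AE interruption over 28 days | Withdrawn from the study (7.1.2) | Off treatment (7.2.1); not a withdrawal reason (7.2.2); withdrawal means withdrawn consent (7.0) | No, as to study status |

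**Scope of the reduced-dose sentence.** Table 7-1 covers related events and separates hematologic from non-hematologic ones. The 7.1.2 sentence does neither. Read literally, it reaches an unrelated or disease-related Grade 3 event.

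**Footnote letters.** In the text as read, the Grade 3 and Grade 4 non-hematologic cells carry b and c, while the printed notes are a and b. Moving each mark back one letter puts the Grade 3 note on the Grade 3 cell and the Grade 4 note on the Grade 4 cell. The mismatch may come from reading the PDF. The last three rows of the table do not depend on it.

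**Effect on drug exposure.** In the first three rows, one rule ends dosing and the other allows it to continue or restart. In the last row, the patient is off drug under both rules, so only study status and follow-up differ.

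**Size per patient.** The documents give no rate of these events in MDS, so the number of patients affected cannot be estimated. At the planned N = 45 (Protocol 9.3):

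- Discontinuation rate: one reclassified patient moves it by 1/45 = 2.2 points, two by 2/45 = 4.4, three by 3/45 = 6.7.
- Primary response rate, taking the planned 40% as an illustration: 0.40 × 45 = 18 responders, so 18/45 = 40.0%. If one non-responder drops out of the Efficacy Evaluable Set, it becomes 18/44 = 40.9%. If one responder drops out, it becomes 17/44 = 38.6%.

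The SAP reports early termination and does not state the number treated. With fewer than 45 patients, each share is larger.

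**The case against.** The strongest reply is that the text is softer than the table above suggests. Table 7-1 is headed as suggestions, 7.1.1 gives the investigator discretion, and the reduced-dose sentence in 7.1.2 says should. Some variation between sites is therefore intended. That stands for the table. It does not reach the no-retreatment sentence in 7.0, the over-28-day sentence in 7.1.2 or the list of mandatory reasons in 7.2.1, and discretion cannot satisfy two opposite mandatory sentences.

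A second reply is that the Grade 4 footnote is an ordinary exception to its cell with a slipped letter, and that a patient resumed under it was never permanently discontinued. This is plausible, but neither the cell nor 7.0 says so. A third is that 7.1.2, being specific to reduced-dose patients, overrides the general table. That is a sensible reading, but the precedence is not stated, and it does not remove the clash within 7.1.2 between discontinuation and restart.

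A reader might also infer more than the documents support:

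- **That one toxicity can lead to a permanent stop, a restart, no change or removal from the study.** It cannot. No change is never offered for Grade 4, and removal depends on an interruption over 28 days, not on grade.
- **That the over-28-day conflict affects who is on drug at Week 24.** It does not, as shown above. Section 7.0 also asks for the end-of-treatment and safety follow-up visits when a patient is discontinued from participation.
- **That SAP 4.1.1 would count such a patient twice by mistake.** It tabulates treatment discontinuation from the End of Treatment form and study discontinuation from the End of Study form. A patient may properly appear in both.
- **That a dose level below 200 mg is missing.** Two 200 mg tablets make 400 mg, and the one named reduction of 50% gives 200 mg. For a new Grade 3 or higher event at the reduced dose, 7.1.2 points to discontinuation, and recurrence of the original event may also lead there. The documents do not call for a further step.
- **That such events must be frequent because entry allows low counts.** No rate is given. Protocol 8.7.1 and 8.7.3 limit which fluctuations and laboratory findings become AEs, and the second conflict requires an earlier dose reduction.

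**Conclusion.** The contradictions are real in three separate situations, and the sentences concerned need to be reconciled. The first two can change who stays on treatment and who enters the Efficacy Evaluable Set. The third changes only study-discontinuation status and follow-up. At the planned size, each reclassified patient is worth 2.2 points of a discontinuation rate. In the 40% illustration, a patient moved out of the primary analysis set shifts the response rate by 0.9 points (non-responder) or 1.4 points (responder). How many patients are affected is unknown.

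The conclusion rests on taking treatment discontinuation in its 7.2.1 sense throughout section 7. It does not rest on the footnote letters. Early termination limits the benefit for future dosing, but the classification question remains for the report, and SAP section 5 does not address it. Which clinical rule should stand is for the sponsor's clinical team.

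**What to change.** Reconcile 7.0, Table 7-1, 7.1.2, 7.2.1 and 7.2.2 so that each situation has one rule:

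- Make the Grade 4 non-hematologic cell, the resume footnote and the no-retreatment sentence agree, and correct the footnote letters.
- State whether the 7.1.2 reduced-dose sentence covers related events only, whether it covers hematologic events, and whether it takes precedence over Table 7-1.
- Use one term for a stop that allows a restart and another for a permanent stop.
- Give an interruption over 28 days for a related AE the same study status in every section, and apply it consistently to the End of Treatment and End of Study forms behind SAP 4.1.1.

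Settle the disposition status before database lock and record it in the SAP. If any patient is still being dosed, amend the protocol wording and send a site letter. The cost is wording only, with no added patients, visits or tests.
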